5.3.2.1.2. Data Included

All available data from randomized participants that have received at least one dose are included (ITT analysis set in Part 2), after taking into account all the ICEs and applying the ICE strategies in Section 5.3.2.

5.3.2.1.3. Assumptions

- Missing Data for HDV RNA and ALT are Missing At Random (MAR)
- The treatment effect is homogeneous across strata

5.3.2.1.4. Missing Data Handling Rule

- Participants who withdraw from the study prior to Week 48 will be considered as non-responders.
- For participants who remain in the study at Week 48 after experiencing a major protocol deviation defined for the purpose of efficacy analyses, which is an ICE, and have missing HDV RNA and/or ALT values at Week 48, then the imputation to non-response will be applied. If the value for the primary endpoint at Week 48 is available, then such data will be used to determine their response status.
- For participants who remain the study at Week 48 and have had no major protocol deviations defined as ICE and have the values of HDV RNA and ALT available, such data will be used to determine their response status.
- For participants who remain in the study at Week 48 and who have not experienced any major protocol deviations defined for the purpose of efficacy analyses as ICE, and has missing HDV RNA and/or ALT values missing at Week 48, then the primary method to handle missing data will be the Multiple Imputation (MI) approach³ under the assumption of MAR, applied in a joint fashion to leverage the correlation between HDV RNA and ALT values over time.

The multiple imputation (MI) model will use all available data and be applied to the continuous HDV RNA and ALT values (not the binary endpoint). Of note, also the pre-ICE data for those subjects who experienced an ICE will be included in the MI model; but for these subjects the response status will be applied according to the ICE strategies before running the MI model.

The model will include treatment, the 3 randomization factors, the available non-missing log-transformed HDV RNA data (values < LLOQ, < LOD TND or < LOD TD will be first substituted following the main rules described in Table 4, ALT values for each scheduled time point (Week) and the following demographic and baseline characteristics^{4,6}: age, gender, and baseline value for HDV RNA level, ALT level, HBsAg level, and HBV DNA level.

Depending on the amount of missing data, the number of imputed datasets to be generated will be 10 and will be adjusted appropriately to ensure robustness in the results⁵.

5.3.2.2. Sensitivity Estimators of the Main Estimand for the Primary Endpoint

Sensitivity analyses will be conducted by constructing a different sensitivity estimator for the primary estimand as defined in Section 5.3.2. The estimator will use Missing as Non-Response data imputation rule.

5.3.2.2.1. Sensitivity Estimator of the Main Estimand (Missing as Non-Response) for the Primary Endpoint

For this sensitivity estimator, the same statistical model (stratum-adjusted MH test) and data included will be used as for the main estimator (Section 5.3.2.1). The assumption for missing data and the rule to handle missing data have changed.

5.3.2.2.1.1. Assumptions

- Missing Data for HDV RNA and ALT are Missing Not At Random (MNAR)
- The treatment effect is homogeneous across strata

5.3.2.2.1.2. Missing Data Handling Rule

Participants who withdraw from the study prior to Week 48 will be considered as non-responders. All participants with missing data for the determination of the primary endpoint will be imputed as non-responders.

5.3.2.3. Supplementary Estimators of the Main Estimand for the Primary Endpoint

Supplementary analysis to better interpret the primary analysis results will be conducted by constructing additional estimator for the main estimand of the primary endpoint as defined in Section 5.3.2. This estimator will be based on the mITT set (instead of ITT) for participants in Part 2. To provide a comprehensive interpretation of the study results and the impact of COVID-19 pandemic, the following supplementary estimator will utilize the mITT analysis set for participants in Part 2. The supplementary estimator analysis will only be performed if there is a difference of more than 5% from ITT to mITT.

5.3.2.3.1. **Supplementary Estimator (mITT + Missing as Non-Response) of the Main Estimand for the Primary Endpoint**

For this supplementary estimator, the same estimand defined in Section 5.3.2, statistical model (stratum-adjusted MH test) and assumptions will be used as for the main estimator (Section 5.3.2.1).

5.3.2.3.2. **Data Included**

All available data from mITT analysis set in Part 2, after taking into account all the ICEs and applying the ICE strategies specified in the previous Section 5.3.2, will be included.

5.3.2.3.3. **Assumptions**

- Missing Data for HDV RNA and ALT are Missing Not At Random (MNAR)
- The treatment effect is homogeneous across strata

5.3.2.3.4. **Missing Data Handling Rule**

The missing data approach will follow the missing as non-response approach as described in Section 5.3.2.2.1.2.

5.3.3. **Subgroup analyses**

Subgroup analyses will be performed on the primary endpoint by the subgroups defined in Section 2.4.1. Subgroup analyses, as exploratory, will be conducted on Part 2 data alone as well as combined data (Part 1 and Part 2) to leverage the total sample size of the entire study. They will only be performed if their size is more than 10% of the total sample size.

The potential association between the primary efficacy endpoint and the selected demographic and baseline characteristics (in Section 2.4.1) will be explored using a logistic regression model which will be estimated for each subgroup variable, one at a time. The factors in each model will be treatment arm, the randomization stratification factors, the subgroup variable, and the treatment-by-stage and treatment-by-subgroup variable as the interaction-terms. The Firth's penalized likelihood method^{9,10} (as implemented in SAS PROC LOGISTIC) will be used in the logistic regression to reduce possible bias which could arise in the presence of a zero-response rate in one or more subgroup levels and/or intervention arms.

Corresponding 95% CIs will be also calculated. A forest plot will present graphically the endpoint estimates resulting from the models described above, by treatment arm and the prespecified subgroup levels, with the corresponding 95% CIs.

5.4. **Key Secondary Endpoints (KSE)**

All key secondary endpoints will be summarized individually by intervention arm, stage and study parts (Parts 1 and 2, as well as for the whole study data overall). The statistical analysis will follow the estimand and estimators framework as described in the following sections. Testing will be performed by providing adjusted p-values as per Section **Error! Reference source not found.**

5.4.1. KSE1: HDV RNA Decline from Baseline $\geq 2 \log_{10}$ IU/mL or HDV RNA TND at Week 48

5.4.1.1. Definition

The first key secondary efficacy endpoint (KSE 1) is defined as the proportion of participants with HDV RNA decline $\geq 2 \log_{10}$ IU/mL from baseline or HDV RNA TND at Week 48.

5.4.1.2. Main Estimand for the KSE1

Study Objective: To evaluate the efficacy of JNJ-3989 + NA regimen versus Placebo + NA in reducing HDV replication.

Scientific question: in the adult population co-infected with HBV and HDV, what is the benefit of JNJ-3989 (100mg Q4W) in combination with NA compared with Placebo + NA for 48 weeks in reducing HDV replication?

The main analysis of this endpoint will be addressed by using the following estimand attributes:

A) Study Intervention:

- Arm 1: JNJ-3989+NA
- Arm 2: NA alone

B) Study population: Non-cirrhotic patients 18 to 65 years of age, inclusive, with HBV/HDV co-infection.

C) Variable: Response status defined as having HDV RNA decline $\geq 2 \log_{10}$ IU/mL from baseline or HDV RNA TND at Week 48

D) Intercurrent events:

- Treatment discontinuation prior to Week 48: if the participant discontinued treatment prior to Week 48 then the participant will be considered as non-responder (composite strategy).
- Selected major protocol deviations affecting efficacy: 0 identifies deviations considered as ICEs. Participants with such deviations and who have missing data for HDV RNA at Week 48 will be considered as non-responders (composite strategy).
- Deaths prior to Week 48 are handled in a composite strategy as participants who die prior to Week 48 will be considered as non-responders.

E) Population level summary: Difference in proportion of responders defined by KSE 1 between the two intervention arms.

5.4.1.2.1. Main Estimator of the Main Estimand for the KSE1

5.4.1.2.1.1. Analysis Methods

Statistical Model

The same stratum-adjusted MH test on the difference of proportions as described for the main estimator of the main estimand for the primary endpoint will be used (see Section 5.3.2.1).

5.4.1.2.1.2. Data Included

All available data from ITT analysis set in Part 2, after taking into account all the ICEs and applying the ICE strategies specified in the previous Section 5.4.1.2, will be included.

5.4.1.2.1.3. Assumptions

- Missing Data for HDV RNA are Missing At Random (MAR)
- The treatment effect is homogeneous across strata

5.4.1.2.1.4. Missing Data Handling Rule

- Participants who withdraw from the study prior to Week 48 will be considered as non-responders.
- For participants who remain in the study at Week 48 after experiencing a major protocol deviation defined for the purpose of efficacy analyses, which is an ICE, and have missing HDV RNA at Week 48, then the imputation to non-response will be applied. If the value for the primary endpoint at Week 48 is available, then such data will be used to determine their response status.
- For participants who remain the study at Week 48 and have had no major protocol deviations defined as ICE and have the values of HDV RNA available, such data will be used to determine their response status.
- For the participants who remain in the study at Week 48 and who have not experienced any major protocol deviations defined for the purpose of efficacy analyses as ICE, and has missing HDV RNA values missing at Week 48, then missing data will be imputed by the values obtained from the MI model performed for the main estimator of the primary efficacy endpoint to leverage the correlations between HDV RNA and ALT values (see Section 5.3.2.1.4). Once the HDV RNA values at Week 48 are obtained, the binary key secondary endpoint will be derived and analyzed as described in Section 5.3.2.1.

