5.3.2. Main Estimand for the Primary Endpoint

Primary Study Objective: To evaluate the efficacy of JNJ-3989 + NA regimen versus Placebo + NA in reducing HDV replication and associated liver inflammation.

Scientific question: in the adult non-cirrhotic population co-infected with HBV and HDV, what is the benefit of JNJ-3989 (100mg Q4W) in combination with NA compared with Placebo + NA for 48 weeks in reducing HDV replication measured by HDV RNA and liver inflammation measured by ALT?

The main estimand for the primary endpoint is characterized by the following attributes:

A) Study Intervention:

- Arm 1: JNJ-3989 + NA
- Arm 2: Placebo + NA

B) Study population: Non-cirrhotic patients 18 to 65 years of age, inclusive, with HBV/HDV co-infection

C) Variable: Response status defined as having HDV RNA decline $\geq 2 \log_{10}$ IU/mL from baseline or HDV RNA TND in combination with normal ALT at Week 48

D) Intercurrent events (ICEs):

- Treatment discontinuation prior to Week 48: if the participant discontinued treatment prior to Week 48 then the participant will be considered as non-responder (composite strategy).
- Selected major protocol deviations affecting efficacy: 0 identifies deviations considered ICE. Participants with such deviations and who have missing ALT and/or HDV RNA data for the primary endpoint at Week 48 will be considered as non-responders (composite strategy).
- Deaths prior to Week 48 are handled in a composite strategy as participants who die prior to Week 48 will be considered as non-responders.

E) Population level summary: Difference in proportion of responders defined by the primary endpoint between the two intervention arms (Arm 1 – Arm 2).

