5.4.2.2.1. Main Estimator of the Main Estimand for the KSE2

5.4.2.2.1.1. Analysis Methods

Statistical Model

The same stratum-adjusted MH test on the difference of proportions as described for the main estimator of the main estimand for the primary endpoint will be used (see Section 5.3.2.1).

5.4.2.2.1.2. Data Included

All available data from ITT analysis set in Part 2, after taking into account all the ICEs and applying the ICE strategies specified in the previous Section 5.4.2.2, will be included.

5.4.2.2.1.3. Assumptions

- Missing Data for ALT are Missing At Random (MAR)
- The treatment effect is homogeneous across strata

5.4.2.2.1.4. Missing Data Handling Rule

- Participants who withdraw from the study prior to Week 48 will be considered as non-responders.
- For participants who remain in the study at Week 48 after experiencing a major protocol deviation defined for the purpose of efficacy analyses, which is an ICE, and have missing ALT at Week 48, then the imputation to non-response will be applied. If the ALT value for the KSE2 at Week 48 is available, then such data will be used to determine their response status.

- For participants who remain the study at Week 48, have had no major protocol deviations defined as ICE and have the values of ALT available, such data will be used to determine their response status.
- For the participants who remain in the study at Week 48 and who have not experienced any major protocol deviations defined for the purpose of efficacy analyses as ICE, and has missing ALT values missing at Week 48, then missing data will be imputed by the values obtained from the MI model performed for the main estimator of the primary efficacy endpoint to leverage the correlations between HDV RNA and ALT values (see Section 5.3.2.1.4). Once the ALT values at Week 48 are obtained, the binary key secondary endpoint will be derived and analyzed as described in Section 5.3.2.1.

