5.4.4.2. Main Estimand for the KSE4

Study Objective: To evaluate the efficacy of JNJ-3989 + NA regimen versus Placebo + NA in reducing liver fibrosis.

Scientific question: in the adult population co-infected with HBV and HDV, what is the benefit of JNJ-3989 (100mg Q4W) in combination with NA compared with Placebo + NA for 48 weeks in reducing liver fibrosis determined using LSM?

The main analysis of this endpoint will be addressed by using the following estimand attributes:

A) Study Intervention:

- Arm 1: JNJ-3989+NA
- Arm 2: NA alone

B) Study population: Non-cirrhotic patients 18 to 65 years of age, inclusive, with HBV/HDV co-infection

C) Variable: Response status defined as having reduction in LSM from baseline ≥ 2 kPa at Week 48 as assessed by VCTE (Fibroscan)

D) Intercurrent events:

- Treatment discontinuation prior to Week 48: if the participant discontinued treatment prior to Week 48 then the participant will be considered as non-responder (composite strategy).
- Selected major protocol deviations affecting efficacy: 0 identifies deviations considered as ICEs. Participants with such deviations and who have missing data for LSM at Week 48 will be considered as non-responders (composite strategy).
- Deaths prior to Week 48 are handled in a composite strategy as participants who die prior to Week 48 will be considered as non-responders.

E) Population level summary: Difference in proportion of responders defined by KSE3 between the two intervention arms.

5.4.4.2.1. Main Estimator of the Main Estimand for the KSE4**5.4.4.2.1.1. Analysis Methods****Statistical Model**

The same stratum-adjusted MH test on the difference of proportions as described for the main estimator of the main estimand for the primary endpoint will be used (see Section 5.3.2.1).

5.4.4.2.1.2. Data Included

All available data from ITT analysis set in Part 2, after taking into account all the ICEs and applying the ICE strategies specified in the previous Section 5.4.4.2, will be included.

5.4.4.2.1.3. Assumptions

- Missing Data for LSM are Missing At Random (MAR)¹²
- The treatment effect is homogeneous across strata.

5.4.4.2.1.4. Missing Data Handling Rule

- Participants who withdraw from the study prior to Week 48 will be considered as non-responders.

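### The KSE1 rule for participants with an intercurrent-event deviation points to the primary endpoint (HDV RNA plus normal ALT), although KSE1 is defined on HDV RNA alone

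*SAP*

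**What the plan says.** SAP 5.4.1.1 makes KSE1 a purely virological endpoint: it "is defined as the proportion of participants with HDV RNA decline $\geq 2 \log_{10}$ IU/mL from baseline or HDV RNA TND at Week 48". The estimand in 5.4.1.2 keeps to this. Its variable (item C) is HDV RNA response. Item D handles deviations that count as intercurrent events without mentioning ALT: "Participants with such deviations and who have missing data for HDV RNA at Week 48 will be considered as non-responders (composite strategy".

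The operational rule is in 5.4.1.2.1.4. For a participant with such a deviation who remains in the study at Week 48, missing HDV RNA leads to non-response. Where data exist, the rule is: "If the value for the primary endpoint at Week 48 is available, then such data will be used to determine their response status". The next bullet, for participants without such a deviation, goes back to the right marker (the excerpt stops just before the words for their KSE1 outcome): "have had no major protocol deviations defined as ICE and have the values of HDV RNA available, such data will be used to determine their".

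The primary endpoint variable in 5.3.2 is different, because it adds ALT (the excerpt stops just before the week number): "Response status defined as having HDV RNA decline $\geq 2 \log_{10}$ IU/mL from baseline or HDV RNA TND in combination with normal ALT at Week".

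**The concern.** KSE1 is the endpoint that shows HDV suppression separately from liver inflammation, which KSE2 covers. A rule that takes KSE1 status from the primary endpoint brings ALT back in for one subgroup, the participants with an intercurrent-event deviation. Two participants with the same HDV RNA response and the same abnormal ALT would then be scored differently according to whether one had, say, missed several NA doses. The sentence also leaves a gap: where ALT is missing, a responder on HDV RNA may have no primary endpoint value to draw on. A programmer following the rule as written, and one following the estimand, could produce different KSE1 results from the same data.

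**Working it through.** The plan states no figure to reproduce here. The check compares the texts and then gives the scale of one misclassification.

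**Parallel rules for deviators with data**

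- Primary (5.3.2.1.4): uses the primary endpoint value, which is correct there.
- KSE1 (5.4.1.2.1.4): the same sentence word for word, not adapted.
- KSE2 (5.4.2.2.1.4): adapted to its own marker, "If the ALT value for the KSE2 at Week 48 is available, then such data will be used to determine their response status".
- KSE3 (5.4.3.2.1.4): names HBsAg.
- KSE4 (5.4.4.2.1.4): names LSM.

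KSE1 is the only key secondary endpoint whose rule does not name its own marker.

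**All nine Week 48 combinations** for a participant with an intercurrent-event deviation who is still in the study and on treatment (1 = KSE1 responder, 0 = non-responder):

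| HDV RNA | ALT | Estimand, 5.4.1.2 | 5.4.1.2.1.4 read literally |
|---|---|---|---|
| response | normal | 1 | 1 |
| response | abnormal | 1 | **0** |
| response | missing | 1 | **no bullet applies** |
| non-response | normal | 0 | 0 |
| non-response | abnormal | 0 | 0 |
| non-response | missing | 0 | 0 if primary non-response is inferred from HDV RNA alone; otherwise no bullet applies |
| missing | normal | 0 | 0 |
| missing | abnormal | 0 | 0 |
| missing | missing | 0 | 0 |

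In the third row, the imputation bullet needs missing HDV RNA and the last two bullets need the absence of a deviation. If the primary analysis's own imputation (5.3.2 D, 5.3.2.1.4) were carried across instead, this participant would be a non-responder, which also disagrees with the KSE1 estimand.

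Every primary responder is also a KSE1 responder, so using the primary status can only turn a 1 into a 0. If the sentence named HDV RNA, all nine rows would agree with the estimand.

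**Who is affected.** All of the following must hold:

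- a deviation marked as an intercurrent event in Attachment 1 (items 9 to 16);
- still in the study and on treatment at Week 48, because discontinuation and death already mean non-response under 5.4.1.2 D;
- Week 48 HDV RNA available and showing a response;
- ALT abnormal or missing.

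**Scale of one misclassification.** Part 2 has 30 participants (1.4) randomized 4:1 (1.2). Assuming an exact split:

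- Arm 1: 30 × 4/5 = 24, so one participant is 1/24 = 4.2 percentage points.
- Arm 2: 30 × 1/5 = 6, so one participant is 1/6 = 16.7 percentage points.

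These are shifts in the crude arm proportion. The stratum-adjusted difference would move by an amount that depends on the strata.

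**The case against.** The strongest reply is that this is a copying slip and the rest of the KSE1 text shows what is meant. The definition, estimand items C and D, the missing-data assumption, the other data bullets and the sensitivity rule in 5.4.1.2.2.1.2 all rest on HDV RNA. The data-included paragraph in 5.4.1.2.1.2 also refers back to the strategies of 5.4.1.2. On that reading the primary endpoint data are only a condition, response status follows item C, and an HDV RNA responder with abnormal ALT counts as a KSE1 responder. This stands in part: the misclassification depends on the literal reading. But if the availability of the primary endpoint value is the condition, a responder with missing ALT still falls under no bullet of the rule. The gap closes only by setting the sentence aside in favour of the estimand.

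It is also fair to say that the same HDV RNA endpoint is summarized over time on observed cases, without ALT (5.5.1.1.1), so a reader would have a cross-check. And 1.3 makes the analyses descriptive, so no confirmatory conclusion turns on this.

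Three stronger inferences are tempting and are not supported:

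- **A large effect, because about half of Part 1 had ALT elevations.** That figure (Amendment 3 rationale) concerns on-treatment elevations in 22 Part 1 participants, occurring at or before Week 16 and not split by arm. It does not give the frequency of abnormal ALT at Week 48 among Part 2 deviators.
- **A bias against Arm 1.** This is plausible if HDV RNA responses are mainly in Arm 1, but it is not shown. A misclassification in Arm 2 would widen the difference instead.
- **KSE4 analysed on the wrong endpoint.** Its summary measure reads "Difference in proportion of responders defined by KSE3 between the two intervention arms", and KSE3 is now HBsAg seroclearance. Amendment 4 swapped the two positions, and item C of the KSE4 estimand explicitly defines response as LSM reduction. This is stale numbering.

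**Conclusion.** The sentence in 5.4.1.2.1.4 is wrong as written and should be corrected. It contradicts the KSE1 definition, the KSE1 estimand and the next bullet. Under the literal reading one combination of results is misclassified (HDV RNA response with abnormal ALT). One is certainly left without a rule (HDV RNA response with missing ALT). Any misclassification lowers the KSE1 rate in the arm concerned.

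The size is about 4.2 points per affected participant in Arm 1 or 16.7 points in Arm 2, assuming a 24 to 6 split. The number affected cannot be derived from the SAP and may be zero, so no total effect can be claimed. The harm is bias or ambiguity in a descriptive estimate. It is neither a loss of type I error control nor evidence that the plan meant to include ALT in KSE1.

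**What to change.** In 5.4.1.2.1.4, replace the reference to the primary endpoint value with the HDV RNA value for KSE1 at Week 48, and add that this holds regardless of ALT. The rule then matches estimand items C and D for every combination of results.

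As clean-up only, correct the endpoint numbers left over from the KSE3/KSE4 swap: KSE4 to KSE3 in 5.4.3.2.1.4, and KSE3 to KSE4 in 5.4.4.2 E) and 5.4.4.2.1.4.

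The cost is a few words of SAP text. If the KSE1 derivation is already programmed, check the one line that assigns status to deviators with Week 48 data. No data collection or other analysis changes.
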